14.12 Overdose

Drug overdose should be reported in the same format and within the same timelines as an SAE, even if they may not result in an adverse outcome. In the event of overdose, the patient should be observed closely for signs of toxicity. Appropriate supportive treatment should be provided if clinically indicated.

AFM13 overdose is defined as any dose administration where $> 10\%$ over 7 mg/kg is administered whether or not associated with an AE.

If the pharmacy discovers that an overdose has or may have been administered, they should contact the Study Investigator and Study Coordinator

14.13 Laboratory Assessments

Blood and urine samples will be collected for the following analyses:

- Complete Blood Count
- Serum Chemistry
- Urinalysis

A serum pregnancy test will be done on all women of childbearing potential; a negative test result must be obtained prior to the first administration of study treatment.

Samples will be collected per institutional procedures and analyzed in the local laboratory.

14.14 Biological Parameters/Markers

Specifications for collection and handling of samples for the assessment of biological parameters/markers, are included in the Immunobiology Research Manual.

Biological parameters/markers will be analyzed according to the scope of work and laboratory capabilities at Principal Investigator's study center. Additional analyses will be performed at contract service laboratory facilities as detailed in the Immunobiology Research Manual.

14.15 Electrocardiogram Assessments

A resting 12-lead ECG will be done to assess the patient's general suitability for therapy as well as to record her/his initial status to enable assessing treatment-related toxicities that may occur later on.

ECGs will be performed after 5 minutes rest, in the supine position.

In case of pathological findings a printout of ECG is required.

Additional cardiac function tests may be required in case of suspected cardiac malfunction that warrants further investigation.

14.16 Physical Examination

Physical examinations shall include those areas of general physician assessment including but not limited to the skin, lymph nodes, spleen, and liver. Performance status and body weight should be assessed once weekly.

Further examinations may be necessary based on the patient's condition and are in the responsibility of the investigator.

Any new or worsening clinically significant changes have to be reported on the appropriate AE or SAE form.

14.17 Vital Signs

Assessment of vital signs will include temperature, systolic blood pressure, diastolic blood pressure, heart rate and respiratory rate per institutional standard of care prior to, during, and after each dosing.

Vital signs will be measured after 5 minutes rest, in the supine position

14.18 Assessment of Pharmacokinetics

Specifications for collection and handling of samples for PK assessments are included in the Immunobiology Research Manual. For adequate analysis of PK at one time point a blood sample of approx. 3 ml is required for analyses at CUMC. Additionally, PK assessments will be performed at Affimed's contract laboratory services in Germany.

PK analyses will be done in the center laboratory at CUMC, for analyses done locally.

Full PK assessments will include but may not be limited to estimates/calculations of:

- maximum measured plasma concentration (C_{max})
- area under the curve (AUC)
- distribution volume V_D
- terminal half-life
- clearance

15 STATISTICAL EVALUATION

15.1 Statistical Methods

The data will be analyzed by the Columbia University Medical Center. This is a single center study. The data will be summarized with respect to demographic and baseline characteristics, biological activity measurements, safety observations, efficacy observations, PK and potential biomarker observations. The data will be presented by dose cohorts and overall. The clinical database lock will occur after all data are reconciled (i.e. “cleaned”) for all patients. A single clinical study report will be generated for this study. The Statistical Analysis Plan (SAP) will be finalized and signed before the database lock.

The data analysis will take place after the time of database lock when all patients have completed 2 cycles or discontinued the study prior and all data is cleaned. Further data for patients that are followed up past the two cycles will be summarized in an extension report once all patients have discontinued the study. All analyses are of exploratory nature.

15.2 Sample Size and Power

The planned total target accrual for this study is 15 subjects.

As this study is of exploratory nature no formal sample size calculation is done. However based on the prior phase I study of AFM13, it is expected that approximately 78% of the patients will show biological activity. Observing 12 patients out of 15 with biological response would lead to 95% exact binomial confidence interval of (52%, 96%). The lower bound of 52% is assumed to be sufficient for evidence of biological activity in this exploratory study.

15.3 Study Populations

Since this study is of exploratory nature only one data set is defined for all analysis.

The **safety set** consists of all patients that have received at least one dose of AFM13.

Patients will be analyzed in the cohort of the treatment they have actually received. Cohorts will be disjoint sets; each Patient will belong only to one cohort. For the primary outcome the analysis population will be a subgroup of the safety set, only patients with baseline measurements and have completed cycle 1 will be considered.

15.4 Demographics, Baseline Characteristics and Medical History

Demographics, baseline characteristics and medical history will be analyzed for the safety set by cohort and overall. For continuous variables, descriptive statistics will be presented including: mean, standard deviation, median and range. For categorical variables frequency and percentages will be presented. All data will be listed.

15.5 Treatment, Compliance, Disposition, Concomitant Therapies, Protocol Deviations

As a compliance measure the actual number of doses of AFM13 received will be summarized by dose cohort. The reason for discontinuation of study treatment and study including study completed as per protocol will be presented. Concomitant medication will be coded by ATC terminology and summarized by frequencies. Patients with major protocol deviations as defined by the study team prior to database lock will be summarized. The safety set will be used. All data will be listed.

15.6 Primary Objective

The primary objective of the study is to evaluate the biological effects of AFM13 in tumor and peripheral blood. For this, NK immunophenotypic characterization, proliferation, density, activation and effector function (cytokine production and release, ADCC) will be measured in peripheral blood. More importantly, intratumoral NK-cell infiltrate and density, phenotypic characterization, cytokine production and release will also be analyzed in the tumor. Similarly, T cells will be assessed for the same phenotype, activation and effector function (including CTL) both in the peripheral blood and the tumor tissue. Finally, cancer cells will be studied for CD30 expression, immunological receptors and other tumor markers. Other tumor resident immune cells will also be characterized (myeloid-derived suppressor cells, Tregs). Details of immunological and biological studies to be conducted in this protocol appear in the Immunobiology Research Manual.

These endpoints will be assessed by visit and presented by change from baseline. Mean, standard deviation, median and range will be calculated for continues measurements, frequency and percentages for categorical data. Correlation of biological and clinical outcome will be assed graphically. Non-parametric tests for change over time such as the Friedman-test and the signed rank test might be facilitated, however no adjustment for multiplicity is planned. All data will be listed. Only patients in the safety set that have also completed cycle 1 and have biopsies obtained at 2 scheduled time points for biopsy collection will be assessed and presented. No imputation of missing values is planned.

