9.4 Number of Subjects

The study will enroll 15 evaluable subjects. Evaluable patients are defined as having 1 biopsy pre-treatment and at least 1 biopsy post treatment.

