Assessments made on drug administration days are to be conducted prior to the start of study medication infusion, unless specified otherwise

Patients with clinical benefit (SD, PR, CR) will receive a second cycle starting after week 11.

All study procedures have a +/- 3 day window, unless otherwise specified.

§ Restaging is to be done at each Week 11 Visit +/- 2 weeks.

- a. AFM13 is infused over 4 hours at the first infusion day. Infusion duration is to be stepwise reduced by 30 min to a minimum of 1 hour at the following infusion days. Cave: measures related to infusion duration in case of adverse events. In cohort 3 weekly treatment will consist of a loading AFM13 dose of 1 mg/kg to be applied on day 1 as 1-hour infusion, followed by a 6 mg/kg AFM13 as continuous infusion over 5 days.
- b. Pregnancy test done at screening must be within 7 days of treatment initiation.
- c. A histological confirmation of CD30-positive lymphoma can be made using the previous tumor biopsy (paraffin-embedded tissue block and slides).
- d. Physical examination will include recording the patient's weight and height at Screening and weight at the End of Study visit. Symptom-directed physical examinations at other time points are to be done as needed.
- e. Additional ECGs will be obtained if clinically indicated. All ECGs will be done on local equipment.
- f. Vital signs include temperature, systolic blood pressure, diastolic blood pressure, heart rate and respiratory rate.
- g. Collected prior to all infusions, during Cycle 1 only
- h. Blood samples for full PK to be taken for cohort 1, 2 and 4 prior to infusion and at the following times points after end of first infusion on Week 1 Day 1 and Week 5 Day 1 only: 0, 2, 4, and 24 +/- 4 hours, for cohort 3: prior to infusion and at the following time points after end of the loading dose on Week 1 Day 1 and Week 5 Day 1 only: 0, 2, 4, and 24 +/- 4 hours
- i. Skin biopsies on Day 1, pre-treatment (can be taken -7 days from day 1) and 5 (can be taken -1 day from day 5 or up to +3 days) should be taken from different lesions, if possible. If this is not possible, the biopsy on Day 5 should be taken from as far away as possible from the first one (at least 3 cm).
- j. Blood needs to be centrifuged and serum to be frozen.
- k. Blood for cytokines has to be taken prior to infusion, at the end of infusion and 2 hours after end of infusion on Week 1 Day 1, Week 4 Day 1 and Week 8 Day 1. Optional sample will be collected upon PD or EoS.

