10.10 Risk/Benefit and Ethical Assessment

The field of immune-oncology has been fueled by recent approvals of biological agents (i.e., mAbs,) for therapy of malignant melanoma, lung cancer, ovarian cancer so far (ipilimumab, nivolumab, pembrolizumab) [38-40]. Because tumor development and growth is known to be associated with failure of the immune system in its surveillance capacity, it has become increasingly clear that immunological and biological factors must exist in the body that either promote tumor development, provide growth advantage and survival, and/or abrogate the ability of the nascent malignant cell or that of the established tumor to survive the immunological attack. Knowledge of these factors is crucial to our understanding of how to refine the dose and schedule of our current drugs and drug candidates in order to develop more efficacious therapies. The main aim of this study is to identify and characterize immunological and biological factors that may correlate with clinical activity or resistance to therapy. Again, this knowledge is vital to our future efforts to design rationally drugs that are likely to have a positive clinical outcome for patients with lymphoma.

This study is to be conducted in patients with histologically-confirmed CD30-positive lymphoma with cutaneous presentation that has relapsed or is refractory to at least 1 prior therapy for the current disease, and has no further standard therapy available (Brentuximab Vedotin is only FDA approved in HL and ALCL with no approval in other lymphomas). AFM13 is a bispecific tetravalent CD30/CD16A chimeric antibody (TandAb) developed for the treatment of CD30-positive malignancies, and has shown promising anti-tumor responses in HL patients with relapsed or refractory HL [29, 34]. AFM13 is a novel drug candidate for CD30-positive lymphoma, which restricts its use in the current study to patients who have no further standard therapy available.

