10.14 Replacement of Subjects

Patients whose mandatory biopsies are not obtained during cycle 1, will be replaced, though the individual patient may continue their therapy if it is deemed that they are deriving benefit from it.

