13.3 Definitions

Evaluable for objective response. Patients who complete 1 cycle of therapy according to the study protocol, and have had their disease re-evaluated will be considered evaluable for response. When no imaging/measurement is done at all at a particular time point, the patient is not evaluable at that time point. Similarly, patients whose tumour assessments are not repeated/incomplete will also be considered non evaluable for response. Patients evaluable for response will have their response classified according to the definitions stated below. Patients who exhibit objective disease progression prior to the end of Cycle 1 will also be considered.

Table 6: Global Response Score

Global Score*	Definition	Skin	Nodes/Blood/Viscera
CR	Complete disappearance of all clinical evidence of disease	CR	All categories have CR/NI
PR	Regression of measurable disease	CR	All categories do not have a CR/NI and no category has a PD
		PR	No category has a PD and if any category involved at baseline, at least one has a CR or PR
SD	Failure to attain CR, PR, or PD representative of all disease	PR	No category has a PD and if any category involved at baseline, no CR or PR in any
		SD	CR/NI, PR, SD in any category and no category has a PD
PD	Progressive disease	PD	PD in any category
Relapse	Recurrence disease in prior CR		Relapse in any category

CR=complete response; NI=noninvolved; PD=progressive disease; PR=partial response; SD=stable disease

*It is recommended that not only the proportion of patients who achieve a response or an unfavorable outcome be calculated but a life table account for the length of the interval during which each patient is under observation also be generated.

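### Sections 15.3 and 15.6 restrict the primary biological summaries to cycle 1 completers, so early leavers who are evaluable under 9.4 are left out despite usable paired data

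*Combined protocol and SAP*

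**What the plan says.** - **15.3 Study Populations.** For the primary outcome, "only patients with baseline measurements and have completed cycle 1 will be considered".
- **15.6 Primary Objective.** "Only patients in the safety set that have also completed cycle 1 and have biopsies obtained at 2 scheduled time points" are to be assessed and presented. This covers blood and tumour endpoints alike. They are summarised by visit as change from baseline, with no imputation, and all data are listed. It adds: "Correlation of biological and clinical outcome will be assed graphically".
- **9.4 Number of Subjects.** The target is 15 evaluable subjects. "Evaluable patients are defined as having 1 biopsy pre-treatment and at least 1 biopsy post treatment". There is no completion condition.
- **Table 2, footnote i.** "Skin biopsies on Day 1, pre-treatment (can be taken -7 days from day 1) and 5", the latter with a window of one day earlier to three days later, so Day 4 to Day 8. Section 10.3 takes blood for immunology, cytokines and sCD30 at both W1D1 and W1D5.
- **10.14 Replacement of Subjects.** "Patients whose mandatory biopsies are not obtained during cycle 1, will be replaced". The protocol does not say which biopsies are mandatory.
- **Ways to leave cycle 1 early.** These include progression, unacceptable toxicity and withdrawal of consent (10.13), a delay of more than 3 weeks (12.8) and a drug-related Grade 4 AE (12.9).
- **Other populations.** Section 15.7.4 (PK) needs only a baseline and one post-baseline value. Section 15.7.1 (ORR) uses the safety set with response as defined in 13.3, which makes completing one cycle the main condition for evaluability but adds: "Patients who exhibit objective disease progression prior to the end of Cycle 1 will also be considered".

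**The concern.** Completing cycle 1 is a post-baseline event that can depend on how the patient responds to or tolerates the drug. Conditioning the primary summaries on it can bias the described biological effect. The bias is upward if those who leave are mostly inactive, and downward if patients who stop for toxicity are biologically active.

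The graph of biology against outcome is also affected. Section 10.10 gives the main aim as identifying "immunological and biological factors that may correlate with clinical activity or resistance to therapy". A patient whose progression is recognised during cycle 1 is informative about resistance and may have a full Day 1 and Day 5 set of tissue and blood, yet would not appear. Results are shown by cohort, and the planned cohorts have 3 patients (one grows to 6 with the expansion in 9.1), so a single exclusion is a large part of a cohort.

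**Working it through.** **1. Who is excluded.** Take a patient with biopsy and blood at W1D1 and W1D5 who is withdrawn in, say, week 3.

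| Rule | Condition | Result |
|---|---|---|
| 9.4 | one biopsy before and one after treatment | evaluable |
| 15.3 | baseline, cycle 1 completed | out |
| 15.6 | dosed, biopsies at 2 time points, cycle 1 completed | out |

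A completer who has only the same two biopsies meets 15.6. The two patients have the same paired data and differ only in clinical course, so the condition does not select on data completeness.

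**2. Whether replacement cures it.** There are two readings of 10.14.
- If only the first pair is mandatory, the leaver is not replaced, fills one of the 15 places and is not analysed.
- If every scheduled cycle 1 biopsy is mandatory (10.4 also lists W4D1, W6D1 and W8D1), a new patient may restore n. The leaver's data still stay out, and 10.14 then disagrees with 9.4.

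**3. Effect on the quantity 15.6 plans.** Let n patients have a value at a visit, of whom k are later leavers. Let the leavers' mean change differ by d (in between-patient SDs) from that of those who stay, m.

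Mean of all = m + d·k/n; mean of completers = m; shift from exclusion = d·k/n in size.

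For k = 1 and d = 1 (assumed):
- 3-patient cohort: 1/3 = 0.33 SD
- 6-patient cohort (3 + 3): 1/6 = 0.17 SD
- overall (4 × 3 + 3 = 15): 1/15 = 0.07 SD

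Here n includes the leaver. If the leaver is also replaced, n rises by one and the shifts are d/4, d/7 and d/16. They apply only at visits the leaver attended, for example Day 5. At later visits the leaver has no value under either rule, so nothing changes.

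**4. What-if on the 15.2 illustration.** Section 15.6 names no binary response endpoint, so this only gives a sense of scale. The exact 95% limits are the 0.025 quantile of Beta(x, n−x+1) and the 0.975 quantile of Beta(x+1, n−x).

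Plan's figure: 12/15 = 80.0% (51.9% to 95.7%), which reproduces the stated 52% to 96%.

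Assume 15 completers are analysed with 12 active, and k replaced leavers with paired data are added back:

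| k | all leavers inactive | all leavers active |
|---|---|---|
| 1 | 12/16 = 75% (48–93%) | 13/16 = 81% (54–96%) |
| 2 | 12/17 = 71% (44–90%) | 14/17 = 82% (57–96%) |
| 3 | 12/18 = 67% (41–87%) | 15/18 = 83% (59–96%) |

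If instead one leaver is among the 15 and is not replaced, the completer result is 12/14 = 86% (57–98%) if that patient was inactive, or 11/14 = 79% (49–95%) if active.

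**The case against.** A completer set has a rationale. The endpoints are repeated measures over cycle 1, and a fixed group keeps the time course free of changing patient mix. The Friedman test, which 15.6 mentions as an option, needs complete series. This stands as a reason to keep completers as a secondary set. It does not justify discarding a Day 1 to Day 5 change, which needs no later visit.

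The study is exploratory and tests no hypothesis, so error rates are not at issue. All data are listed, and 15.5 reports reasons for discontinuation. With about 15 patients a careful reader could find the excluded values. That makes the loss visible but does not put these patients into the summaries or the graph.

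A reader might infer that resistant patients are generally missing from the graph. The documents do not support that. Scheduled restaging is at Week 11 (10.5, 10.6), after the 8 treatment weeks, so a patient who stays on treatment and whose progression is found there is not lost. Only progression recognised sooner, for example in the skin at a weekly visit, leads to exclusion.

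A reader might also infer that the rest of the plan is free of such selection. It is not: 13.3 has its own one-cycle condition, relaxed only for early progressors. The cleaner contrasts are with 9.4 and with the PK rule in 15.7.4.

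**Conclusion.** The conflict in the text is certain: 15.3 and 15.6 exclude patients whom 9.4 calls evaluable, on a post-baseline criterion, and 10.14 does not bring them back. It should be fixed before the SAP is signed.

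The size and direction of any bias are not known, because the documents give no leaver rate. The d/3, d/6 and d/15 shifts rest on one leaver and an assumed difference d, and hold only at attended visits. The binomial figures rest on assumed numbers of leavers who are all active or all inactive.

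Two stronger inferences should be resisted. The first is that reported activity will be inflated, or that the 52% lower bound fails: one inactive leaver would lower the bound to 48% and one active leaver would raise it to 54%, and neither is an endpoint that 15.6 plans. The second is that loss will concentrate at 7 mg/kg: 9.2 reports more frequent and more severe infusion reactions at that dose, not more discontinuations.

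**What to change.** In 15.3 and 15.6, remove completion of cycle 1 from the primary population and state:
- **Tumour endpoints:** all dosed patients with a pre-treatment and at least one post-treatment biopsy (the 9.4 rule).
- **Blood endpoints:** all dosed patients with a baseline and at least one post-baseline sample (the 15.7.4 rule).
- **Replaced patients** who meet these rules stay in.
- **10.14:** define mandatory biopsies so that the term agrees with 9.4.
- **Reporting:** n at each visit, and exclusions with reasons by cohort.
- **Sensitivity set:** cycle 1 completers, for the time course and any Friedman test. Define completion, including how skipped doses (12.8) and an early stop followed by a Week 11 return (12.9) are classed.

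The cost is protocol and SAP wording; no new samples or visits are needed. There are three downsides. The number and mix of patients will differ between Day 5 and later visits, so attrition could look like a time trend, and trends should be read in the completer set. Some selection remains, because a post-treatment sample is still required. The reported figure may also be slightly less favourable.

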15.7 Secondary Objectives

15.7.1 Efficacy

Clinical efficacy will be estimated by ORR defined by achieving CR and/or PR, as defined in Section 13.3. For the overall cohort 95% exact binomial confidence intervals will be presented. The safety set will be used. All data will be listed.

